#### SOURCES OF PATIENTS IV.

Patients will enter the Registry as a result of: (1) screening consecutive exams in the laboratories of participating institutions (i.e., echocardiographic, radionuclide, and cardiac catheterization laboratories) to identify patients with an ejection fraction of 45% or less; or (2) by a survey of the consecutive hospital discharge records to identify patients with a diagnosis of congestive heart failure (CHF). In order to qualify for the Registry, patients identified from source (2) should have radiological evidence of CHF (or signs of pulmonary venus congestion) or an ejection fraction of 45% or less.

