# V. ENTRY AND EXCLUSION CRITERIA

## Entry Criteria

Patients are eligible for the Registry if they either have an ejection fraction less than or equal to 45% or a diagnosis of congestive heart failure. The date of their logbook record or hospital admission must fall within the specified nine-month timeframe (for example, from January 1, 1988 to September 30, 1988). A diagnosis of congestive heart failure will be confirmed if the patient has radiologic evidence of CHF.

Descriptive statements consistent with heart failure which may appear in the report include:

- a) Statements related to pulmonary blood flow redistribution to upper lobes.
- b) Signs of pulmonary venous congestion
  - Basal or perihilar vascular blurring
    - Alveolar or pulmonary edema
    - Kerley B lines
    - Pleural effusion judged secondary to congestive heart
    - failure (to make this judgment may require correlation with clinical data).
- c) Cardio-thoracic ratio will be included whenever possible.

SOLVD Registry Protocol November 1987

In validating these heart failure criteria as positive, the interpretation on the chest X-ray report should be accepted if it is definite. Follow-up reports indicating clearing of congestive heart failure are helpful. Films should be reviewed by a physicianinvestigator whenever uncertainty exists.

Particular attention will be given to the subset of patients entering with the syndrome of pulmonary edema unrelated to acute myocardial infarction. Diagnosis should be (relatively) easily confirmed in this subset and the clinical history data on a large volume of patients with pulmonary edema could be a valuable contribution by this registry.

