## Exclusion Criteria for SOLVD Registry

1) Non-valvular congenital heart disease.

2) Any noncardiac life-threatening disease likely to significantly shorten the patient's survival, including criteria 11 (cor pulmonale), 12 (advanced pulmonary disease), 13 (major neurologic diseases), 17 (renal failure), 18 (malignancies), 21 (significant primary liver disease), and 23 (other life-threatening disease) in the SOLVD trials protocol.

3) Failure to consent to the Registry.

Lack of a telephone or reliable means of contact/follow-up.

5) Myocardial infarction within 7 days. This patient can be included after 6 days have passed, if there is a qualifying chest X-ray or ejection fraction measurement made 7 or more days after the MI.

6) Cardiac surgery, PTCA, or ballon valvuloplasty within 7 days. This patient can be included after 6 days have passed, if there is a qualifying chest X-ray or ejection fraction measurement made 7 or more days after the cardiac surgery or PTCA.

Thus, the following exclusion criteria from the SOLVD trials protocol are not exclusion criteria for the Registry:

- History of intolerance to enalapril 1
- Currently taking ACE inhibitor and unwilling to discontinue 2
- Hemodynamically significant valvular or outflow tract 4 obstruction
- Constrictive pericarditis 5
- Syncopal episodes presumed to be due to life-threatening 7 arrhythmias
- Any major cardiac surgery likely 8
- Unstable angina pectoris 9
- 10 Uncontrolled hypertension
- Cerebrovascular disease 14
- Collagen vascular disease other than rheumatoid arthritis 15
- Suspected significant renal artery stenosis 16
- Immunosuppressive therapy 19
- 20 Active myocarditis
- Likely to be nonadherent (alcoholism, drug addiction, lack of 22 of a fixed address, etc.)
- Woman likely to bear children 24
- Other investigational drug protocols (except compassionate use) 25
- Failure to give consent for the SOLVD trials 26
- Lack of adherence or tolerance to medication 27
- Lack of adherence to placebo run-in 28

Note also that patients scheduled for cardiac transplantation are eligible for the ' Registry. Given all these differences, the patient population of the Registry will thus be broader and less restrictive than those eligible for the Trials.

- - - -

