### Appendix A

### A1: SOLVD REGISTRY FLOW DIAGRAM

.4

			19
	SOLVD	REGISTR	
	BASEL	NE FORM	
	11/1	1/87	
REGISTRY ID:	FOR	i: R B F VERS	SION: A VISIT: 0
INSTRUCTIONS	This form is to be completed on all consecut using only the information available from the To be eligible for the Registry, the patient a diagnosis of congestive heart failure configuration Please print clearly when entering a response eral Instructions for Completing Forms for com-	a appropriate medical reco must either have an EF <= firmed by radiologic eviden te into the boxes. See the	rds. 45% or have hce.
	· •		
	SOLVD MAIN REGISTRY BASELINE FORM	(screen 1 of 15) (RBF pag	e 1 of 8)
A. IDENTIFY	ING INFORMATION	B. ELIGIBILITY ASSESSMEN	T Unrec
1.1 Today's	Date:/ // // /	
 
Most recently measur (should be 7 or more diac surgery, FTCA,
 
	ed Ejection Fraction days after an MI, car- or balloon valvuloplasty):
1.2 Initial	s of person completing form:	3.1 Percentage:	
2.1 Last Nam		3.2 Date://	Day / The Year
2.2 First N		3.3 Hethod utilized:	Radionuclide R Contrast angiography A 2-D echo E
2.3 Middle 1	Initial:		Not on chart U

2 (1.1. 1) (1.1. 1) (1.1. 1) (1.1. 1)

• .

•

				1			
	Yes	No l	Inrecorded	c.	DEMOGRAPHIC INFORMATION		
4.1	Primary diagnosis of heart failure and chest X-ray consistent with heart failure (X-ray should be 7 or			6.	Sex:	Male Female	M F
	more days after an MI, cardiac surgery, PTCA, or balloon valvuloplasty) Y	N	υ	7.	Ethnic Identity	American Indian	1
1. 9	Date of multiplan Y-news					Asian	2
4.4	Date of qualifying X-ray:					Black	3
	Month Day Year					Caucasian	4
53 1000				1		Hispanic	5
5.	Reasons for exclusion from Registry					Other	6
5.1	Presence of non-valvular congenital heart disease Y	N	U			Not on chart	7
5.2	Presence of any non-cardiac life- threatening disease which is unlikely to allow the patient to survive one year (Includes 11, 12, 13, 17, 18, 21 and 23 of SOLVD trials)	N	υ	8.	Date of Birth:	Year	
5.3	No telephone or reliable means of contact/follow up Y	N	υ	9.	Social Security Number (Ca (IMPORTANT!! MUST BE COMPL		):
5.4	Failure to consent to Registry Y	N	U		-	-	
5.5	Is patient eligible for Registry? Y (If NO, exit form)	N				Bagan antanan da na vindu na	-

SOLVD MAIN REGISTRY BASELINE FORM (screen 3 of 15) (RBF page 2 of 8)

10.1 Participant Street Address:	10.5 Zip Code/Canadian or European Postal Code:
	11. Participant Telephone Number (Home):
	HOSPITAL INFORMATION
10.2 City:	12.1 Hospital name:

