10.3 State/Province:	12.2 Hospital street address:
10 4 Country:	

12.3 City:	14.2 First Name:
	15.1 Street address:
12.4 State/Province:	
12.5 Country:	
12.6 Zip Code/Canadian or European Postal Code:	15.2 City:
13. Patient hospital ID number:	
PRIVATE PHYSICIAN INFORMATION	15.3 State/Province:
14.1 Last Name:	15.4 Country:
	15.5 Zip Code/Canadian or European Postal Code:

4

SOLVD MAIN REGISTRY BASELINE FORM (screen 5 of 15) (RBF page 3 of 8)

•

16. Telephone Number (private physician):	19.1 Street address:
NEAREST RELATIVE OR FRIEND NOT RESIDING WITH PARTICIPANT	
17.1 Last name:	
	19.2 City:
17.2 First name:	
18. Relationship:	

(Nearest relative/friend continued)	D. X-RAY FINDINGS Ye	s
19.3 State/Province:	<pre>21.1 Is chest-X-ray available? Y    (If NO, skip to section E)</pre>	
19.4 Country:	21.2 Date of most recent chest X-ray (should be 7 or more days after MI, cardiac sur- gery, PTCA, or balloon valvuloplasty): ////// Month Day Year	
20. Telephone number:	21.3 Is this X-ray the qualifying X-ray? Y	
	22. Pulmonary congestion:	
	22.1 Evidence of pulmonary congestion Y (If NO, skip to Q. 23)	!
	22.2 Basal or perihilar vascular blurring	!
	22.3 Kerley B lines Y	!
	(continued)	

Т

SOLVD MAIN REGISTRY BASELINE FORM (screen 7 of 15) (RBF page 4 of 8)

	Y	es	No			Yes	No	Unreco
	Alveolar or pulmonary edema		N	24.	Indicate all of the following th rently (including etiology speci	at o fied	ccur abo	concur ve):
22.5	Pleural effusion	Y	N	24.1	Ischemic heart disease (IHD)	Y	N	U
E.	ETIOLOGY OF DISEASE	223		24.2	Hypertensive heart disease (HHD)	¥	N	U
23.1	What is the primary etiology of participa heart disease (choose only one of the fol	int's	ng):	24.3	Active myocarditis	Y	N	U
	Ischemic heart disease (IHD)		1	24.4	Idiopathic cardiomyopathy	¥	N	U
	Hypertensive heart disease (HHD)		2	24.5	Specific cardiomyopathy (ex: viral, toxic, ETOH, post-	Y	N	U
	Active syocarditis		3		partum, history of cocaine use) (If NO or UNRECORDED, skip to Q.	24.	7)	
	Valvular heart disease - aortic		4	24.6	Specify:			
	Valvular heart disease - mitral		5	24.7	Valvular heart disease - aortic	Y	N	U
	Idiopathic cardiomyopathy (specifics unknown)		6	24.8	Valvular heart disease - mitral	Y	N	U
	Specific cardiomyopathy (ex: viral, toxic, ETOH, postpartum, history of cocaine use) (If none, skip to Q. 24)		7					
23.2	Specify:		-		•			

-----

F. RELATIONSHIP TO SOLVD TRIALS (SKIP TO SEC G IF EF> 35%)		Yes	No	Unreca
	26.3 Complex congential heart disease	Y	N	U

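### The Registry Baseline Form does not match the protocol text on baseline EF, noncardiac exclusion and the heart-failure route, so cohort and baseline EF may depend on which text a center applies

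*Protocol*

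**What the plan says.** **Time zero and strata.** Section IX (Baseline Data Collection) dates enrollment by the qualifying measurement, and by the earliest one if several qualify. Section II.A stratifies the primary mortality objective by symptoms, etiology, EF and chest X-ray findings at entry. Section X analyzes time from entry to death in a Cox model and names EF among the covariates.

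**What the form captures.** Item 3 of the Registry Baseline Form asks for the most recently measured EF, with its percentage (3.1), date (3.2) and method (3.3). For X-rays, the form records the date of the qualifying film under item 4. Item 21.2 then asks for the "Date of most recent chest X-ray", item 21.3 asks whether that film is the qualifying one, and items 22.1 to 22.5 record the findings.

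**Noncardiac exclusion.** Section V, exclusion 2, reads "Any noncardiac life-threatening disease likely to significantly shorten the patient's survival". Form item 5.2 excludes for life-"threatening disease which is unlikely to allow the patient to survive one year". Both list the same trial criteria; the form's version is "Includes 11, 12, 13, 17, 18, 21 and 23 of SOLVD trials".

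**Heart-failure route.** Section V makes patients "eligible for the Registry if they either have an ejection fraction less than or equal to 45% or a diagnosis of congestive heart failure", with the diagnosis confirmed radiologically. The form's header says the same. Item 4.1 asks for "Primary diagnosis of heart failure and chest X-ray consistent with heart failure".

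**Order of steps.** Section IX has the chart screened for eligibility first, followed by consent and extraction to the form. Item 5.5 then records eligibility and ends the form if the answer is no.

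**The concern.** EF is both a named stratifier and a model covariate. For the mortality rates by EF to mean what Section II.A says, the EF must be the value at time zero. A value measured later exists only for patients who lived long enough to be measured again, and it may reflect recovery or deterioration after entry. If the earliest qualifying EF has no field, the analyst cannot recover it from the form. In a patient who qualified by EF alone, the date that defines time zero is not visibly on the form either.

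The two eligibility items raise a different problem. A center that answers them literally and a center that works from Section V could classify the same patient differently. The outcome is all-cause mortality at one, three and five years, so a noncardiac exclusion tied to one-year survival has least control over noncardiac deaths at the later two time points. The word primary in item 4.1 touches patients with secondary heart failure and no EF of 45% or less. These can include patients with preserved systolic function, whom Section I gives as one reason for having a Registry.

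**Working it through.** **1. The texts side by side**

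| Topic | Protocol text | Form | Patients for whom it matters |
|---|---|---|---|
| EF | Earliest qualifying date sets enrollment (IX); EF at entry (II.A) | Most recent EF (item 3); no visible field for the qualifying EF | Those with more than one EF before the form is completed |
| X-ray | Findings at entry (II.A) | Qualifying date (item 4) and flag (21.3), but findings 22.1 to 22.5 are those of the most recent film | Those for whom 21.3 is No |
| Noncardiac disease | Survival significantly shortened, no horizon (V, exclusion 2) | Survival to one year unlikely (5.2) | Those judged on prognosis; the seven listed criteria are the same in both |
| Heart failure | Any CHF diagnosis with radiologic evidence (IV, V, form header) | Primary diagnosis (4.1) | Those with secondary CHF and no EF of 45% or less |

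**2. One patient traced through.** Suppose a patient qualifies with an EF of 40% and measures 50% before the form is completed. Under Section IX, enrollment is the date of the 40% value. Item 3 records 50% and its later date. The form then shows an EF above the entry limit, measured after time zero, and the 40% value is lost.

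**3. The plan's only whole-Registry figure that uses EF.** Table 1 Case 1 compares EF ≤ .40 with EF > .40: 4500 against 1500 patients, one-year mortality .12 against .05, two-sided 0.05, stated power 1.00.
- Pooled rate: (4500 × .12 + 1500 × .05)/6000 = .1025.
- SE under the null: √[.1025 × .8975 × (1/4500 + 1/1500)] = .00904.
- SE under the alternative: √[.12 × .88/4500 + .05 × .95/1500] = .00743.
- Power: Φ[(.07 − 1.96 × .00904)/.00743] = Φ(7.0) = 1.000. The stated figure reproduces.

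**4. Illustration for EF.** Assume that a share s of each true group is recorded in the other group. Then the low-EF rate is [4500(1−s)(.12) + 1500s(.05)]/[4500(1−s) + 1500s], and the high-EF rate follows in the same way.

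| s (assumed) | Low-EF rate | High-EF rate | RR | Power |
|---|---|---|---|---|
| 0 | .1200 | .0500 | 2.40 | 1.00 |
| 5% | .1188 | .0595 | 1.99 | 1.00 |
| 10% | .1175 | .0675 | 1.74 | 1.00 |
| 20% | .1146 | .0800 | 1.43 | 0.99 |
| 30% | .1113 | .0894 | 1.24 | 0.79 |

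No document gives s, and it cannot exceed the share of patients with a repeat EF. Real drift need not be symmetric.

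**5. Illustration for item 5.2.** Compounding 12% a year gives a three-year mortality of 1 − .88³ = .319. If 3% to 5% of enrollees (assumed) had 50% three-year mortality (assumed), the overall rate would rise by (.50 − .319) × .03 = .005 to (.50 − .319) × .05 = .009, or 0.5 to 0.9 points. With 6000 patients, the SE of that rate is √(.319 × .681/6000) = .006, so the 95% half-width is about 1.2 points.

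**The case against.** The strongest reply is that the form does not decide who enters. Chart screening comes first, the form's header repeats the Section V rule, and items 3 and 4.1 show no exit instruction. This stands. The form records eligibility and gates on it at item 5.5, but it is not the only test.

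A reader might infer that the enrolled cohort is not the one the primary objective describes. The documents do not support that. Section II.A describes only a relatively unselected cohort with heart failure and/or left ventricular dysfunction, the seven listed exclusions agree, and no count of affected patients is given.

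A reader might also infer that a patient expected to live two to four years is plainly out by the protocol and in by the form. That is one reading only. Section V gives no horizon, so item 5.2 can be taken as its working definition, and the listed criteria are defined in a trials protocol that is not shown.

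On X-rays, the form already dates the qualifying film and flags whether the latest film is that one. What remains is that the findings belong to the latest film.

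On EF, item 3.2 dates the value, the laboratory route starts from the qualifying exam itself, and forms are due within 90 days of logbook registration, which limits how late a recorded EF can be. These points narrow the problem without closing it. The date exposes a late EF only if the enrollment date is known from elsewhere, and no date restores the missing qualifying value. It is also fair to say that item 3 conflicts with the enrollment-date rule and with EF at entry, not with an eligibility rule for repeated EFs, because the protocol states none.

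Finally, the shift illustrated for item 5.2 lies within sampling error. That is correct, although a difference in case definition does not shrink as more patients are enrolled.

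**Conclusion.** The mismatches are real and should be corrected before recruitment. The EF item carries the most weight: followed as written, it can supply a stratifier and Cox covariate that post-dates time zero or exceeds 45%, with the qualifying value unrecorded. The likely damage is to EF-specific mortality and relative risk. Power for the main EF contrast falls below 0.99 only when more than about 20% of patients are assumed to be in the wrong group.

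Items 5.2 and 4.1 are contradictions of wording with narrower reach. Read alone, item 5.2 excludes fewer patients than Section V and item 4.1 admits fewer, so no net direction can be stated. The supportable conclusion is that cohort and baseline EF may differ with the text a center applies. How much they differ cannot be derived, and both illustrations rest on assumed shares.

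One caveat: the form's last screen (Section K) is not reproduced in the available text, so the absence of a qualifying-EF field should be confirmed there.

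**What to change.** 1. Add to the form the qualifying EF, meaning the value and date of the measurement that sets enrollment. Keep the most recent EF as a separate item if it is wanted.
2. When item 21.3 is No, record the findings of items 22.1 to 22.5 from the qualifying film as well.
3. State in Section X that strata and Cox models use the EF at enrollment and the qualifying-film findings.
4. Reconcile Section V exclusion 2 and item 5.2 to a single wording.
5. Reconcile item 4.1 with Sections IV and V and the form's header. Which criterion should prevail is for the investigators to decide.

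The cost is a few form fields and matching protocol wording, with no new data source. The form is dated 11/11/87, and recruitment opens January 1, 1988 after a December phase-in and training month, so the change can be made before the first patient is entered.

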### II. AIMS OF THE REGISTRY

### A. Primary Objective:

The primary objective of the Registry is to study all-cause mortality at one, three and five years in a large (approximately 6,000) consecutive and relatively unselected cohort of patients with heart failure and/or with left ventricular dysfunction. The patients will be stratified according to symptoms, etiology of disease, ejection fraction and chest X-ray findings at entry into the Registry.

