## SOLVD MAIN REGISTRY BASELINE FORM (screen 15 of 15) (RBF page 8 of 8)

SOLVD REGISTRY SUBSTUDY BASELINE FORM (screen 1 of 12) (RSB page 1 of 7)

A. IDENTIFYING INFORMATION	B. ECHOCARDIOGRAPHY ELIGIBILITY	Yes
<pre>1.1 Today's date:///</pre>	
 
3.1 Date 2D and M-mode echos done:
 
Month / Day / Year
 
3.2 Were these echocardiograms of good quality? (See protocol for criteria) (If NO, exit form)
 
3.3 Was Doppler echo done? (only for those participants in the Echo Substudy) (If NO, skip to Section C)
 
	Y Y
2.2 Participant's First Name: 2.3 Participant's Middle Initial:	3.4 Date Doppler done: /// Month Day Year	1

Т

c.	ETIOLOGY OF DISEASE AND NYHA CLASS			Yes
4.1	Indicate the primary etiology of the patient's heart disease (choose only ONE of the following):	5.	Indicate all of the following etiologies the have occurred (including the etiology specia bove):	nat ified
	Ischemic heart disease (HD) 1	5.1	Ischemic heart disease (IHD)	Y
	Hypertensive heart disease (HHD) 2	5.2	Hypertensive heart disease (HHD)	Y
	Active myocarditis 3	5.3	Active syocarditis	Y
	Valvular heart disease - aortic 4	5.4	Valvular heart disease - aortic	Y
	Valvular heart disease - mitral 5	5.5	Valvular heart disease - mitral	Y
	Idiopathic cardiomyopathy (specifics unknown) 6	5.6	Idiopathic cardiogyopathy (specifics unknown)	Y
	Specific cardiosyopathy (ax: viral, toxic, ETOH, postpartum, history of cocaine use) 7 (If none, skip to Q. 5)	5.7	Specific cardiomyopathy (ex: viral, toxic, ETOH, postpartum, history of cocaine use) (If NO, skip to Q. 6)	Y
4.2	Specify:	5.8	Specify:	
		6.	New York Heart Association CHF Class: (Choose only one)	

SOLVD REGISTRY SUBSTUDY BASELINE FORM (screen 3 of 12) (RSE page 2 of 7)

Contractor					
		Yes	No		Yes
D.	PAST CLINICAL HISTORY (up to completion			7.9 Hypertension	¥
	of the Registry Baseline form)			7.10 Peripheral vascular disease	Y
7.	Does the participant have a history of:		(restaut)	7.11 Edema	Y
7.1	Pulmonary edema	Y	М	7.12 Breathlessness on exertion	Y
7.2	Diabetes mellitus	Y	M	7.13 Asthma	¥
7.3	Chronic obstructive pulmonary disease	Y	N	(If NO, skip to Q. 8)	
7.4	Cerebrovascular accident	¥	N	7.14 Approximate duration of asthma:	] :
7.5	Angina pectoris	T	M	8. Cigarette smoking (ignore any other tobac	
7.6	Peripheral embolism	¥	M	8. Cigarette smoking (ignore any sther total 8.1 Has the participant ever smoked cigarette	
7.7	Pulmonary embolism	¥	N	regularly? (If NO, skip to Q. 9)	Y
7.8	Syncope	T	N		

•

•

т

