# Appendix D STRATIFICATION FOR SUBSTUDY PARTICIPANTS

It is expected that the vast majority of the participants eligible for the SOLVD Registry will have ischemic or hypertensive heart disease, and that about 5-10% would have cardiomyopathies or other "rare" etiologies. Thus, of the 6000 expected participants for the Registry, approximately 300-600 participants would be of the "rare" etiologies, and 5400-5700 would be of the more common etiologies.

The Registry has the potential to provide valuable clinical history information on the so-called "rare birds" of congestive heart failure. Given the interest in obtaining complete and detailed baseline information on these patients, the computer program for identifying those patients to be included in the Registry Substudy will essentially sample the Registry participants with two different sampling proportions: 100% of the rare etiologies would be included in the Substudy, and somewhere around 7-13% (approximately 400-700 participants) of the ischemic heart disease participants would be included in the Substudy, to roughly complete the 1000 patient desired.

Essentially, the Substudy subsample is a stratified random sample of the Registry sample, with two strata (ischemic heart disease, other) with different sampling proportions (.07-.13, 1.00, respectively).

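### The primary-etiology item has no code for an undetermined or other cause, so such patients can be filed as idiopathic cardiomyopathy or left as an uninterpretable blank

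*Protocol*

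**What the plan says.** Section II.A makes etiology one of four stratification factors of the primary objective: "The patients will be stratified according to symptoms, etiology of disease, ejection fraction and chest X-ray findings at entry into the Registry". Section X names it again as a Cox covariate and as a subgroup factor.

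The variable comes from item 23.1 of the Registry Baseline Form, which asks for the primary etiology of the patient's "heart disease (choose only one of the fol" (the extracted line breaks there). The codes are ischemic, hypertensive, active myocarditis, valvular aortic, valvular mitral, code 6 "Idiopathic cardiomyopathy (specifics unknown", and code 7, specific cardiomyopathy. Below code 7 stands the line "If none, skip to Q. 24", followed by the free-text field 23.2. Item 24 then asks about each etiology with Yes, No or Unrecorded. The Baseline Form is to be completed "using only the information available from the" medical records. Substudy item 4.1 repeats the seven codes, including "Idiopathic cardiomyopathy (specifics unknown) 6".

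Appendix D closes by describing the Substudy as a stratified random sample "with two strata (ischemic heart disease, other"), sampled at .07-.13 and 1.00.

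**The concern.** Charts without an established cause are to be expected. Under Sections IV and V a patient can enter from a laboratory log on an EF of 45% or less, and Section VII states that EF or chest X-ray is the only uniformly required investigation. The nurse who abstracts such a chart must choose one of seven named causes or leave the item empty. Code 6 is the only one whose label contains the word unknown.

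If some of these patients are coded 6, mortality in idiopathic cardiomyopathy describes a mixture of diagnosed disease and patients whose cause was never settled. That touches the etiology strata of the primary objective and the EF-tertile comparison within idiopathic cardiomyopathy (Section VI, Cases 10-11). The same code can also carry them into the Substudy stratum that is taken in full because its diseases are rare. No later analysis can fully separate what the form did not record.

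**Working it through.** **1. Is the omission the form's general practice?** No. Items of the Registry Baseline Form side by side:

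| Item | Other code | Not-recorded code |
|---|---|---|
| 3.3 EF method | none seen | Not on chart |
| 7 Ethnic identity | yes | Not on chart |
| 24.1-24.8 concurrent etiologies | free text for specific cardiomyopathy (24.6) | Unrecorded |
| 23.1 primary etiology | free text for specific cardiomyopathy (23.2) | none |

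**2. Where can an undetermined chart go?**

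- *Code 6.* Nothing directs the nurse there, but nothing prevents it. Item 24 is to include the etiology already given in 23.1, so code 6 implies Yes at 24.4 and the uncertainty is lost.
- *Blank.* The line "If none, skip to Q. 24" can mean that no listed cause applies, or only that no specific cardiomyopathy needs naming in 23.2. Its position under code 7 favors the second reading, and item 24.5 has a parallel line, "If NO or UNRECORDED, skip to Q". A blank may then be undetermined, a cause outside the list (constrictive pericarditis, for example, which Section V does not exclude), or an omission. Unrecorded answers throughout item 24 would identify some of the undetermined.

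**3. Substudy sampling.** Under Appendix D's closing rule, code 6 falls in the stratum sampled at 1.00. A blank is also not ischemic and could be treated the same way, but the selection program's handling of a blank is not stated.

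**4. Illustration of the effect on Case 11.**

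Inputs from Section VI and Table 1: 333 patients per EF tertile, one-year mortality *a* = .06 and *b* = .12, two-sided 0.05, stated power .77.

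Formula, with p̄ = (a+b)/2:

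- s₀ = √(2p̄(1−p̄)/n)
- s₁ = √((a(1−a)+b(1−b))/n)
- power = Φ((|b−a| − 1.96 s₀)/s₁)

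Reproduction: p̄ = .09, s₀ = .02218, s₁ = .02206, so Φ((.06 − .04347)/.02206) = Φ(.749) = .773, which matches .77. Case 10 (.05 against .15) gives .991, which matches .99.

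Assumptions not in the documents: a share *f* of the group is undetermined, it is spread evenly over the tertiles, and its one-year mortality is 12% in both tertiles (12% is a rate used in Table 1, borrowed here). Each tertile's rate becomes (1−f)·rate + f·.12.

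| f | Rates, Case 11 | Relative risk | Power, 333 per tertile |
|---|---|---|---|
| 0 | .060 / .120 | 2.00 | .77 |
| .10 | .066 / .120 | 1.82 | .67 |
| .20 | .072 / .120 | 1.67 | .56 |

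Case 10 falls less, from .99 to .97 and .92.

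These figures keep the group at 1000, so undetermined patients replace true idiopathic ones. If they came on top of 1000 true cases, the tertiles would hold 1000/(.9×3) = 370 or 1000/(.8×3) = 417 patients, and the same formula gives .72 and .65 for Case 11. Power falls either way, and the estimated relative risk shrinks by the same amount.

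**The case against.** - **The label can be read narrowly.** Code 6 stands directly above specific cardiomyopathy, so its parenthesis may mean only a cardiomyopathy without a specific cause. This is fair. It shows that code 6 was probably not meant as a catch-all, but it leaves an undetermined chart without a code.
- **Guidance may exist elsewhere.** The form refers to general instructions and a manual that are not shown, abstractors are experienced nurses, and training is scheduled. A rule there could reduce the problem. It could not create a code that the form lacks.
- **Other data help.** Prior infarction, angina, revascularization and Q-wave infarction are recorded, and clinical data are collected again directly in Substudy patients. These allow a check for ischemic disease inside code 6. They do not show whether the chart stated an idiopathic diagnosis, and item 4.1 has the same seven codes.
- **Overall mortality is untouched.** True. Only the etiology factor is affected.

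A reader might go further and infer that undetermined patients *do* enter the idiopathic stratum, that they form a sizeable share of it, that they take a large part of the 1000 Substudy places, or that they are older or have hidden ischemic disease. The documents support none of this. No text sends such patients to code 6, a partial exit exists, no share of undetermined charts is given, and nothing describes their age or disease. Selection is not entry either: the Substudy also requires clinic attendance, consent and a good-quality echocardiogram. Appendix D's opening paragraph places hypertensive disease with the common etiologies, so its closing two-stratum wording is not a firm statement of how every non-ischemic patient is sampled.

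**Conclusion.** The point holds as a defect of data capture that creates a risk of misclassification. A single-choice item that feeds a primary-objective stratum lacks an undetermined and an other code, on a form that provides a not-recorded answer for sibling items. Code 6 and an ambiguous blank are the only places left for such charts, and item 24 repairs this in part at best.

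The size cannot be derived from the documents. The loss in Case 11 from .77 to .67 or .56 is illustrative and rests on the assumed 10% or 20% share, the borrowed 12% mortality, even spread over tertiles and a fixed group size. Full sampling into the Substudy is possible under Appendix D's closing rule, but is not established for a blank. The change is worth making because it costs little before abstraction, while later correction would mean returning to the charts.

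**What to change.** - **Item 23.1:** add the codes Undetermined / not on chart and Other (specify).
- **Item 4.1:** add Undetermined and Other (specify). The not-on-chart wording does not suit this item, because its data are collected directly at the visit.
- **Code 6, both forms:** drop the parenthesis, or reserve the code for a stated diagnosis of idiopathic cardiomyopathy.
- **Skip line:** reword it so that it only bypasses the free-text field.
- **Appendix D:** state that undetermined patients are not in the rare-etiology stratum sampled at 100%, and how the program treats a missing answer.
- **Reporting:** give mortality in undetermined patients as a separate etiology group.

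The cost is two codes on each of two forms, some relabelling and one rule in the selection program. The idiopathic group may become somewhat smaller than the roughly 1000 that Section VI expects, with some loss of precision in Cases 10-11, but it would then represent the diagnosis it names.
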